# Summary Table of Study Protocol

Title	Risk of Hypertension, Acute Myocardial Infarction, and Stroke in Migraine Patients Treated With Migraine Preventive Medications
Protocol version identifier	20200403, Version 1.0
Date of last version of the protocol	NA
EU Post Authorization Study (PAS) Register No	NA
Active Substance	erenumab-aooe
Medicinal Product	Aimovig ® (erenumab-aooe), 70 mg or 140 mg
Device	NA
Product Reference	AMG 334
Procedure Number	BLA 761077
Joint PASS	No
Research Question and Objectives	
 
Describe baseline characteristics of four cohorts of migraine patients initiating a migraine preventive treatment: erenumab-aooe, other monoclonal antibodies (mAbs) targeting the calcitonin gene- related peptide (CGRP) pathway, selected standard of care (SOC) antiepileptic preventive medications, and onabotulinumtoxinA.
 
Estimate the risk (cumulative incidence) of three cardiovascular outcomes (hypertension, acute myocardial infarction [MI], and stroke) among new users of erenumab-aooe, other mAbs targeting the CGRP pathway, selected SOC antiepileptic preventive medications, and onabotulinumtoxinA.
 
Assess comparability of migraine patients treated with erenumab-aooe to migraine patients treated with (1) other mAbs targeting the CGRP pathway, (2) selected SOC antiepileptic preventive medications, and 3) onabotulinumtoxinA, with respect to baseline confounders and risk factors for cardiovascular disease.
 
GATED – If appropriate based on comparability analyses, separately compare the risk of acute MI and stroke in patients treated with erenumab-aooe to the risk in each of the other three medication cohorts.
 

Country of Study	United States
Primary Author:	PPD , PhD
	Center for Observational Research
	Email: PPD
Co-Authors	PPD , MD, PhD
	Global Development
	Email: PPD
	PPD , MD
	Global Medical Affairs
	Email: PPD
	PPD , MPH
	Global Safety Email: PPD
	PPD , MD
	US Medical Affairs
	Email: PPD
	PPD , PhD
	Center for Observational Research
	Email: PPD
	PPD , PhD
	Center for Observational Research
	Email: PPD
	PPD , MD
	Global Development
	Email: PPD
	PPD , MD, PhD
	Quantitative Safety and Epidemiology
	Email: PPD
	PPD, MD
	Global Safety
	Email: PPD

### 2. List of Abbreviations

Abbreviation/Acronym	
CGRP	Calcitonin Gene-Related Peptide
CI	Confidence Interval
CPT	Current Procedure Terminology
ER	Emergency Room
FAERS	FDA Adverse Event Reporting System
FDA	Food and Drug Administration
FDAAA	Food and Drug Administration Amendments Act
HCPCS	Healthcare Common Procedure Coding System
ICD-10-CM	International Classification of Disease, Tenth Revision, Clinical Modification
IP	Inpatient
IPCW	Inverse Probability of Censoring Weights
IPTW	Inverse Probability of Treatment Weights
NDC	National Drug Code
NSAIDs	Non-Steroidal Anti-inflammatory Drugs
mAb	Monoclonal Antibody
MI	Myocardial Infarction
OP	Outpatient
PPV	Positive Predictive Value
PS	Propensity Score
RR	Risk Ratio
SOC	Standard of Care
US	United States
USPI	United States Prescribing Information

#### 4. Abstract

• Study Title

Risk of Hypertension, Acute Myocardial Infarction, and Stroke in Migraine Patients Treated with Migraine Preventive Medications

- Study Background and Rationale
- Erenumab-acoe was approved by the United States (US) Food and Drug • Administration (FDA) on 17 May 2018, followed by other monoclonal antibodies (mAbs) targeting the calcitonin gene-related peptide (CGRP) pathway (fremanezumab-vfrm on 14 September 2018, galcanezumab-gnlm on 27 September 2018, and eptinezumab-jimr on 21 February 2020), for the prevention of migraine in adults. On 30 April 2020, new onset hypertension and exacerbation of existing hypertension were added to the Warning and Precautions section of the United States Prescribing Information (USPI) for erenumab-aooe. Regulatory agencies have requested routine post-marketing surveillance data on acute MI and stroke, have required descriptive observational studies on CV outcomes, or have requested additional information for major adverse CV events and hypertension related to use of mAbs targeting the CGRP pathway. In this study, the risk of hypertension, acute MI, and stroke will be estimated in the following four new user cohorts: erenumab-acoe, other mAbs targeting the CGRP pathway, select SOC antiepileptic medications used for migraine prevention, and onabotulinumtoxinA used for migraine prevention. Also, if appropriate based on comparability analyses, gated analyses estimating the relative risk (RR) of acute MI and stroke will be separately conducted for the following three comparisons: (1) erenumab-aooe vs. other mAbs targeting the CGRP pathway, (2) erenumab-aooe vs. selected standard of care (SOC) migraine preventive medications (anti-epileptics), and (3) erenumab-aooe vs. onabotulinumtoxinA.
- Study Feasibility

In a recent internal Amgen study of the MarketScan® Early View database, a total of 15212 erenumab-aooe users, 17239 users of other mAbs targeting the CGRP pathway, and 9242 users of Botox® (onabotulinumtoxinA) were identified from May 2018 through January 2020. Assuming a conservative 3-month growth rate of 15%, the expected number of users of prophylactic migraine medications in the MarketScan® database during the study period (17 May 2018 – 31 May 2020) will be ~20 000 new users of erenumab-aooe, ~23 000 new users of other mAbs targeting the CGRP pathway, and ~13 000 new users of onabotulinumtoxinA.

• Research Question and Objective(s)

Ob	jectives	Endpoints
Pri	mary	
•	To describe baseline characteristics of four cohorts of migraine patients initiating a migraine preventive treatment: erenumab-aooe, other mAbs targeting the CGRP pathway, selected SOC migraine preventive medications (anti-epileptics), and onabotulinumtoxinA.	Not applicable.
•	To estimate the cumulative incidence of hypertension, acute MI, and stroke in migraine patients treated with erenumab-aooe, other mAbs targeting the CGRP pathway, selected SOC migraine preventive medications (anti-epileptics), and onabotulinumtoxinA.	

Hypertension

Acute MI

Stroke

•	To assess comparability of migraine patients treated with erenumab-aooe to migraine patients treated with (1) other mAbs targeting the CGRP pathway, (2) selected SOC migraine preventive medications (anti-epileptics), and 3) onabotulinumtoxinA, with respect to baseline confounders and risk factors for cardiovascular disease, using propensity score (PS) analyses and evaluation of the standardized mean difference for all variables included in the PS model (see Section 8.7.2.4).	Not applicable
•	To assess comparability, separately compare the cumulative incidence of select negative control outcomes among migraine patients treated with erenumab-aooe to migraine patients treated with (1) other mAbs targeting the CGRP pathway, (2) selected SOC migraine preventive medications (anti-epileptics), and 3) onabotulinumtoxinA.	Negative Control Outcomes (see sub-section on negative control outcomes in Section 8.7.2.4)
•	[GATED ANALYSES] If the cohorts are comparable, separately compare the cumulative incidence of acute MI and stroke among migraine patients treated with erenumab-aooe to migraine patients treated with (1) other mAbs targeting the CGRP pathway, (2) selected SOC migraine preventive medications (anti-epileptics), and 3) onabotulinumtoxinA.	

Acute MI

Stroke

Hypotheses/Estimation

We will: (1) estimate the cumulative incidence (95% confidence interval [CI]) of hypertension, acute MI, and stroke (ischemic and hemorrhagic) in initiators of erenumab-aooe, other mAbs targeting the CGRP pathway, selected SOC migraine preventive medications (anti-epileptics), and onabotulinumtoxinA; and, (2) if the cohorts are comparable, we will separately evaluate the null hypothesis of no association between erenumab-aooe versus each of the other new user cohorts on the cumulative incidence (ie, risk) of acute MI and stroke.

• Study Design/Type

Observational retrospective cohort study design.

• Study Population or Data Resource

This analysis will utilize data from the MarketScan® Commercial and Medicare Supplemental medical claims database, which represents the medical experience of insured employees and their dependents for active employees, early retirees, individuals who continue their insurance coverage under the Consolidated Omnibus Budget Reconciliation Act, and Medicare-eligible retirees with employer-sponsored medical supplemental plans. The underlying insured population from which the data are drawn is geographically diverse across the US (47% - South, 18% - North, 17% - West, 20% - North Central), 52% of plan participants are male, and 89% are enrolled in fee-for-service plans.

• Summary of Eligibility Criteria

Patients must be 18-64 years of age on the index date, have one year of continuous medical and pharmacy eligibility prior to and including the index date (ie, the baseline period), and have a diagnosis of migraine during the baseline period. Patients will be excluded from the study if there is any use of a medication targeting the CGRP pathway during the baseline period. In addition, for the SOC migraine preventive medications (anti-epileptics) and onabotulinumtoxinA new user cohorts, patients will be excluded if there was any prior use of the cohort defining medication during the baseline period.

• Follow-up

Follow-up will be evaluated in two ways. With an 'intention-to-treat' analysis, patients will be followed for all available time after they initiate a medication, irrespective of whether they discontinue the medication or not, or whether they switch to an alternate medication or not. Follow-up begins the day after the index date and ends at first occurrence of: (a) the outcome of interest, (b) disenrollment from a health plan, or (c) end of study period. With a 'per-protocol analysis' patients are followed for as long as they are actively taking the medication of interest during the follow-up period. Follow-up begins the day after the index date and ends at first occurrence of: (a) the outcome of interest (each outcome will be assessed independently), (b) disenrollment from the health plan, (c) discontinuation of study medication, (d) switching to an alternate medication, or (e) administrative end of study. For the erenumab-acce and other mAbs targeting the CGRP cohorts, switching occurs when any preventive or acute medication other than the index medication targeting the CGRP pathway is initiated during the follow-up period. For the SOC migraine preventive medications (anti-epileptics) and onabotulinumtoxinA cohorts, switching occurs at initiation of any preventive or acute medication that targets the CGRP pathway during the follow-up period.

- Variables
  - Outcome Variables

The outcomes of interest are hypertension, acute MI, and stroke, which will be identified using ICD-10-CM diagnosis codes.

- Hypertension occurrence of one inpatient (IP) diagnosis, one emergency room (ER) diagnosis, or one outpatient (OP) diagnosis during the follow-up period.
- (2) Acute MI occurrence of one diagnosis in the IP setting during the follow-up period.

- (3) Stroke, including both ischemic stroke and hemorrhagic stroke occurrence of one diagnosis in the IP setting during the follow-up period.
- Exposure Variables New users of:
  - (1) erenumab-aooe,
  - (2) other mAbs targeting the CGRP pathway (fremanezumab-vfrm, galcanezumab-gnlm, eptinezumab-jjmr),
  - (3) selected SOC migraine preventive medications (anti-epileptics) (topiramate, valproic acid, divalproex sodium) which are approved by the Food and Drug Administration (FDA) for the prevention of migraine, and
  - (4) OnabotulinumtoxinA, which is also approved by the FDA for the prevention of migraine.
- Other Covariates

We will assess the following variables during the baseline period: demographics, *a priori* defined covariates of interest, including comorbidities, concomitant medications, and risk factors for the outcomes, and cohort descriptors identified empirically from the most prevalent diagnoses, procedures, and prescriptions.

Study Sample Size

In a recent study of the MarketScan® Early View database, a total of 15212 erenumab-aooe users, 17239 users of other mAbs targeting the CGRP pathway, and 9242 users of onabotulinumtoxinA were identified from May 2018 through January 2020. Assuming a conservative 3-month growth rate of 15%, the expected number of new users during the study period (17 May 2018 – 31 May 2020) will be ~20 000 new users of erenumab-aooe, ~23 000 new users of other mAbs targeting the CGRP pathway, and ~13 000 new users of onabotulinumtoxinA.

Based on these sample size estimates, the 95% CIs for a cumulative incidence for stroke of 0.50% are (0.40%, 0.60%) for erenumab-aooe, (0.41%, 0.59%) for other mAbs targeting the CGRP pathway, and (0.38%, 0.62%) for onabotulinumtoxinA medication users. The 95% CIs and half-widths of the CIs were estimated across a range of cumulative incidence values, assuming varying population sizes, for all three cardiovascular outcomes of interest (hypertension, acute MI, and stroke).

If a comparative analysis is conducted (assuming 20 000 patients in the erenumab-aooe cohort and 20,000 patients in the comparator cohort, a background rate for stroke of 0.60 per 100 person-years (PYs), and an alpha-level of 0.05), a risk ratio of 1.46 would be detected with 80% power. Detectable risk ratios, assuming different population sizes and background rates, were estimated for acute MI and stroke.

• Data Analysis

Baseline characteristics, including the most prevalent diagnoses, procedures, and medication class prescriptions will be summarized for the four study cohorts. Descriptive statistics using mean and standard deviation or median and 25th/75th percentile estimates for continuous variables and number and percentages (n, %) for categorical variables will be used to examine patient characteristics.

The naïve, unadjusted cumulative incidence (ie, risk) of hypertension, acute MI, and stroke will be estimated in the following new user cohorts: 1) erenumab-aooe, 2) other mAbs targeting the CGRP pathway, (2) select SOC migraine preventive medications (anti-epileptics), and (3) onabotulinumtoxinA.

Next, the overlap of the propensity score across treatment groups will be evaluated, the mean standardized difference for all variables included in the propensity score model will be assessed, and a determination will be made on whether null findings are or are not estimated for the negative control outcomes chosen for the study. Comparability between erenumab-aooe and each of the other treatment cohorts will be evaluated separately and each of the comparative analyses will be gated. Specifically, the decision to move forward with the comparative analyses for either the acute MI or the stroke outcome will be made after assessment of covariate balance across treatment groups, whether the negative control outcomes showed treatment associations within the accepted bounds around the null, and sufficient sample size to detect a risk ratio of 2.0 or greater. Analyses will proceed only in the treatment pairs where comparability and sufficient sample size are achieved, and not in others.

Based on the comparability analyses and sample size considerations, the risk of acute MI and the risk of stroke will be separately compared across the following three exposure contrasts: (1) erenumab-aooe vs other mAbs targeting the CGRP pathway, (2) erenumab-aooe vs select SOC migraine preventive medications (anti-epileptics), and (3) erenumab-aooe vs. onabotulinumtoxinA. For these gated analyses, we will utilize inverse probability of treatment weights to account for confounding and inverse probability of censoring weights to account for informative censoring.

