#### Table 1. Baseline Covariates

Footnotes defined on last page of table

Page 4 of 5

Variable	Measurement				
Other Medications (continued)					
Anti-diabetics					
Insulin	0/1 indicator at study entry				
Non-Insulin	0/1 indicator at study entry				
Cardiac glycosides	0/1 indicator at study entry				
Calcium gluconate	0/1 indicator at study entry				
Fludrocortisone/ Midodrine	0/1 indicator at study entry				
Weight loss prescriptions	0/1 indicator at study entry				
Fludrocortisone/ Midodrine	0/1 indicator at study entry				
Hyperpolarization-activated cyclic nucleotide-gated channel blocker	0/1 indicator at study entry				

Table 1. Baseline Co	variates
----------------------	----------

Page 5 of 5

a Health care utilization will also be evaluated as the following time-varying covariate during the follow-up period, evaluated every three months: occurrence of any outpatient visit over the prior three months, occurrence of any ER visit over the prior three months, and occurrence of any inpatient visit over the prior three months. Continuous measures of heath care utilization will also be considered. Medication utilization will be assessed as the number of unique generic medications dispensed during the interval and number of unique drug classes dispensed during the interval.

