The Marketscan® databases contain fully adjudicated eligibility, pharmacy, procedure, and medical claims data for patients enrolled in a large US health plan (IBM Watson, formerly Truven Healthcare). The health plan provides coverage for physician, hospital, and prescription drug services and captures medical claims or encounter data from all available health care sites (inpatient hospital, outpatient hospital, emergency room, physician's office, surgery center, etc.) for virtually all types of provided services. Each facility inpatient admission record contains information on up to sixteen diagnoses (outpatient records contain up to four diagnoses), recorded with ICD-10-CM diagnosis codes and up to sixteen procedures (outpatient records allow for only one procedure) recorded with ICD-10-CM procedure codes, Current Procedural Terminology (CPT), or HCPCS codes. Data are linked at the patient level by a unique identifier that is consistent across services, health plans, and time, and, so, patients can be tracked over multiple years even if they switch health plans when working with a particular employer. Laboratory test results can be linked to the medical and pharmacy claims data for a limited subpopulation of enrollees within the Marketscan® databases. Undiagnosed conditions, and lifestyle and biometric factors (eg, smoking status) are not well captured in claims data. Data are captured when close to 100% of claims have been paid, which results in a lag time between date of service and date of payment of about 3-6 months.

Claims for pharmacy services are typically submitted electronically by the pharmacy at the time prescriptions are filled. The following pharmacy claims data allow for longitudinal tracking of medication refill patterns and changes in medications used:

- NDC or HCPCS
- Medication brand name
- Generic product identifier
- Medication strength
- Quantity prescribed

- Days of supply
- Fill date

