### **Comparability Analyses**

### Estimating the Propensity Score

Next, a linear-logistic model for the conditional probability of treatment,  $Pr(A_i=a|L_i)$ , where  $L_i$  is a vector of measured confounders of the exposure and the outcome, as well as risk factors for the outcome, will be fit (Brookhart et al, 2006). The conditional probability of treatment given a set of covariates is commonly referred to as the propensity score (PS).

For the first set of comparability analyses, overlap of the propensity score across treatment groups will be evaluated. Non-overlap in the PS will be addressed with trimming of subjects at the extremes of the PS distribution. In addition, the mean standardized difference for all variables included in the PS model will be estimated. An absolute mean standardized difference > 0.1 for a given confounder or risk factor for the outcome will be used as a measure of potential imbalance (Austin, 2009; Austin et al. 2007). Covariates in the propensity score model with an absolute standardized difference > 0.1 will be examined for potential inclusion in the outcome model or will be used as evidence of insufficient overlap in the distribution of baseline characteristics across treatment groups. Using PS overlap and cut points for the mean standardized difference to make decisions about cohort comparability are part of an iterative process that potentially involves trimming of subjects (because of poor overlap in the PS) and accounting for confounders in the outcome model rather than the exposure model. As such, this process provides guidance on whether cohorts are comparable and contributes additional information to the body of evidence used to determine whether comparative analyses should be initiated or not.

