### Negative Control Outcome Analyses

Negative control outcome studies are designed to detect and reduce residual bias between treatment groups (Lipsitch et al, 2007, Arnold and Ercumen, 2016). Negative control outcomes are chosen that have no plausible mechanism by which they can be caused by the treatment of interest but do share unmeasured confounders (eg, lifestyle [smoking history, alcohol use], and anthropometric [BMI] variables) with the primary treatment-outcome relation. After controlling for measured confounders, any observed association between the treatment and negative control outcome can be attributed to unmeasured confounding between the groups, rather than a true causal relationship. For example, if the outcome for a comparative safety study is acute MI, the ideal negative control outcomes would share a similar confounding structure as would be hypothesized

for treatment selection (eg, erenumab-aooe vs. other mAbs targeting the CGRP pathway) and the outcome of interest (acute MI). Common outcomes used as negative controls in prior epidemiologic studies of treatments include risks of accidents or hospitalizations for trauma or injury (Dormuth et al, 2009; Brookhart et al, 2007; Jackson et al, 2006).

Selection of migraine preventive treatment is likely affected by many factors associated with a patient's prognosis that can lead to bias when comparing treatment groups in non-interventional settings. Patients initiating newer medications, such as mAbs targeting the CGRP pathway, may have more severe disease and be at higher risk for poor outcomes in comparison to patients initiating other migraine preventive therapies, such as selected SOC migraine preventive medications (anti-epileptics) or onabotulinumtoxinA . It is of interest to understand whether the incidence of clinical outcomes among patients initiating other migraine preventive medications after controlling for measured confounding factors. We will use a negative control study design to investigate this comparability of patients initiating different types of migraine preventive treatments. The results of this analysis will help inform the appropriateness of comparative safety analysis for the two CV outcomes of interest (acute MI and stroke). The negative control outcomes that may be included in the analysis are:

- o Decubitus ulcer
- o Dementia
- o Transfusions
- o Accidents
- Annual wellness visit
- Pelvic exams for cancer screening
- o Influenza vaccine use
- o Mohs surgery

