### **Gated Analyses**

### Estimating the Cumulative Distribution of a Right-Censored Counterfactual Outcome

If appropriate based on comparability analyses, a comparison of the effect of erenumabaooe versus other mAbs targeting the CGRP pathway on acute MI at t=6 months, t=1 year, and t=2 years will be undertaken, where the effect measure of interest is the RR, and the possible sources of bias are confounding and dependent censoring.

First, to address confounding, let  $A_i$  be a discrete random variable denoting exposure to erenumab-aooe (a=1) or other mAbs targeting the CGRP pathway (a=0) for patient i,

and let  $T_i^a$  be the counterfactual time from medication initiation to the acute MI outcome for patient *i*. The counterfactual cumulative incidence of the outcome is then  $R^a(t) = \Pr(T_i^a < t)$ , and the estimate of the RR is:

$$RR(t) = \frac{R^1(t)}{R^0(t)}$$

To account for confounding we will use IPTWs, which will be constructed as follows:

$$\widehat{W}_i^1 = \frac{1}{\widehat{Pr}(A_i = a | L_i)}$$

For the analyses described here,  $Pr(A_i=a|L_i)$  is the conditional probability of treatment (ie, the propensity score described previously). The set of covariates comprising  $L_i$  are listed in Appendix D. The cumulative incidence curves for acute MI, weighted by IPTWs, now account for confounding by measured covariates, but still assume that censoring occurs at random. As previously noted, the risk ratio estimates and 95% confidence intervals at six months, at one year, and at two years will be presented; however, we are also interested in the entire cumulative incidence curve over time. The cumulative incidence curve will be presented graphically.

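### No obesity or BMI diagnosis indicator is pre-specified in Table 1 or the a priori propensity-score list, although the plan names BMI as a confounder

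*Protocol*

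**What the plan says.** The abstract (Other Covariates) lists, among the variables assessed at baseline, a priori "defined covariates of interest, including comorbidities, concomitant medications, and risk factors for the outcomes", and adds "cohort descriptors identified empirically from the most prevalent diagnoses, procedures, and prescriptions". Section 8.7.2.4 (Estimating the Propensity Score) defines the covariate set as one that "is a vector of measured confounders of the exposure and the outcome, as well as risk factors for the outcome". Under Gated Analyses in the same section, the members of that set "are listed in Appendix D".

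BMI appears once as a confounder, in Negative Control Outcome Analyses. Suitable negative controls are those that "share unmeasured confounders (eg, lifestyle [smoking history, alcohol use], and anthropometric [BMI] variables") with the main treatment-outcome relation. Section 8.4 explains the label of unmeasured: "Undiagnosed conditions, and lifestyle and biometric factors (eg, smoking status) are not well captured in claims data".

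Table 1 and Appendix D list many coded comorbidities, among them diabetes, hypercholesterolemia, hypertension, HIV and lupus. The one item in either list that concerns body weight is "Weight loss prescriptions". Appendix D marks it for both the treatment and the censoring model.

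**The concern.** The plan builds the propensity score on confounders and outcome risk factors, and it regards BMI as a confounder. A reader would therefore expect whatever the claims record about body weight to be in the fixed covariate list. Diagnosed obesity can be recorded with ICD-10-CM codes, the same kind of data that supply every other comorbidity flag. A prescription flag picks up drug treatment for weight, which is not the same as diagnosed obesity.

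The balance check decides whether the acute MI and stroke comparisons go ahead, and it covers only variables in the propensity model. If coded obesity is not in the model, an imbalance between erenumab and a comparator is neither weighted on directly nor tested at the 0.1 standardized-difference limit. The negative controls would then have to detect all of it, although part could be handled by adjustment.

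**Working it through.** **Row check.** Table 1 has no obesity, overweight or BMI diagnosis row, and neither does Appendix D. Each has one row on body weight, for weight-loss prescriptions.

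**Routes by which coded obesity could still enter:**

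- Descriptive summary of the most prevalent diagnoses (abstract; section 8.7.2.3.2). An imbalance could be seen there, but this is not part of the balance check.
- Appendix D, footnote a. Common diagnoses may be added to the models; nothing requires it.
- High-dimensional propensity score (section 8.7.2.5.3). It searches ICD-10-CM diagnosis codes but keeps only top-ranked variables, and it is a sensitivity analysis.
- Negative control outcomes. They look for total residual bias and do not adjust for obesity.

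None of these commits the main comparative analysis to including it.

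**Size if obesity were ignored altogether.** The documents state no figure for this, so there is none to reproduce. Rearranged, the formula in section 8.9.1.4 gives

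bias = [RR·p1 + (1 − p1)] / [RR·p0 + (1 − p0)],

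where RR is the confounder-outcome risk ratio and p1 and p0 are the confounder prevalences in the erenumab and comparator arms. All three inputs below are assumptions.

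| RR | p1 | p0 | Calculation | Bias |
|---|---|---|---|---|
| 1.5 | 0.45 | 0.35 | 1.225 / 1.175 | 1.043 |
| 2.0 | 0.45 | 0.35 | 1.45 / 1.35 | 1.074 |
| 2.0 | 0.45 | 0.30 | 1.45 / 1.30 | 1.115 |
| 1.3 | 0.35 | 0.30 | 1.105 / 1.09 | 1.014 |
| 2.0 | 0.50 | 0.30 | 1.50 / 1.30 | 1.154 |
| 2.0 | 0.30 | 0.40 | 1.30 / 1.40 | 0.929 |
| 2.0 | 0.30 | 0.50 | 1.30 / 1.50 | 0.867 |

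The plan accepts bias between 0.91 and 1.10. Among the cases run, bias leaves that band only at RR 2.0, with a gap of at least 15 points when erenumab is higher, or 20 points when it is lower.

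**What an imperfect flag could remove.** Take the third row (bias 1.115), arms of equal size, and a flag with assumed sensitivity 0.50 and specificity 0.97.

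1. Share flagged: 0.45×0.50 + 0.55×0.03 = 0.2415 in the erenumab arm and 0.30×0.50 + 0.70×0.03 = 0.171 in the comparator. The average is 0.20625.
2. Obesity prevalence in the erenumab arm: 0.225/0.2415 = 0.932 if flagged, 0.225/0.7585 = 0.297 if not. In the comparator: 0.15/0.171 = 0.877 and 0.15/0.829 = 0.181.
3. Standardized to the average flag distribution: 0.428 and 0.325.
4. Residual bias: 1.428/1.325 = 1.078.

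On the log scale, 1 − ln(1.078)/ln(1.115) is about 31% of the bias removed. The same steps with sensitivity 0.60 and specificity 0.95 give 1.423/1.328 = 1.071, about 37% removed. With sensitivity 0.30 and specificity 0.97 they give 1.439/1.312 = 1.097, about 15% removed.

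**The case against.** The strongest reply is that the protocol takes a position rather than overlooking BMI. It classes BMI as unmeasured, says biometrics are poorly captured in claims, and assigns the problem to negative controls. Those controls must give more than 90% posterior probability that bias lies within 0.91 to 1.10. Much of this stands, and it rules out three stronger readings.

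- **A reader might infer that a promise is broken.** It is not. The abstract says risk factors will be included, without claiming to include every one, and several major ones are listed.
- **A reader might infer that body-weight information goes unused, or that an imbalance could be neither adjusted for nor seen.** Weight-loss prescriptions are in both models. So are diabetes, hypertension, hypercholesterolemia and their drug classes, which carry part of any effect of obesity. Coded obesity may also surface in the descriptive tables or enter by the optional routes.
- **A reader might infer that a 4% to 12% bias is expected.** The documents supply no obesity prevalence, no obesity risk ratio and no measure of how completely obesity is coded. The calculation also treats obesity as if nothing correlated with it were adjusted for. Two of the three cases behind that range lie inside the plan's tolerance.

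What the reply does not settle is commitment. Poor capture does not mean no capture, and it does not by itself justify leaving out a diagnosis flag. Smoking, also called unmeasured, is given a dedicated bias analysis and a subset of apparent smokers. The optional and sensitivity-only routes do not guarantee that coded obesity is weighted on or tested for balance.

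**Conclusion.** The point stands in a limited form. The plan names BMI as a confounder and builds its propensity score on confounders and outcome risk factors, but pre-specifies no obesity or BMI diagnosis indicator. Its only fixed body-weight proxy is a prescription flag. This is an avoidable gap in the a priori covariate list, not a contradiction. Because the protocol itself fixes that list in Appendix D, it is more than a detail left for later.

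The bias figures show that the issue is worth one covariate and no more than that. They rest on assumed prevalences, an assumed risk ratio and assumed flag accuracy, and they precede any allowance for the covariates already in the model. The actual gain cannot be determined from the documents. The conclusion also rests on obesity being recorded at least partly as a diagnosis in this database, which the protocol neither confirms nor denies.

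**What to change.** Define one baseline obesity indicator from obesity and BMI ICD-10-CM diagnosis codes. Put its code list in Appendix C, add the row to Table 1, and mark it for both the treatment and the censoring models in Appendix D. Check its balance at the 0.1 limit with the other propensity-score covariates. State that recording is incomplete, so adjustment is partial and residual BMI confounding remains with the negative controls. Optionally, apply the bias formula of section 8.9.1.4 to obesity as well as smoking.

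The cost is one more code list and one more covariate, with no new data. If the codes turn out to be sparse, little bias is removed, and the required statement tells the reader so.
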